1 STUDY SYNOPSIS

Title	An Open Label Extension Study of the Safety and Anti-Pruritic Efficacy of Nalbuphine HCl ER Tablets in Prurigo Nodularis Patients
Sponsor	Trevi Therapeutics, Inc. [name] [name] United States [contact] www.trevitherapeutics.com
Protocol Number	TR03ext
Version and Date	Amendment 1: Version 2.0 dated 11 MARCH 2015 Version 1.0 dated 24 JUNE 2014
Indication	Prurigo Nodularis (PN)
Investigational Product	nalbuphine hydrochloride (HCl) extended-release (ER) tablets
Active Ingredient	nalbuphine hydrochloride
Route of Administration	Oral
Duration of Study	The total study duration for any individual patient will be up to 53 weeks. Patients will receive drug treatment for up to 50 weeks.
Study Phase	Phase 2/3
Study Design	Open label
Planned Sample Size	No a priori planned sample size is designated for this study. Eligible patients who have successfully completed the TR03 study and wish to participate in TR03ext may be enrolled, treated, and analyzed. The maximum number of patients will not exceed the number of patients who complete the TR03 study (i.e., up to 60 patients)
Total Number of Centers	Up to 10 sites in North America and Europe
Primary Objective	
 To evaluate the safety and tolerability of nalbuphine HCl ER tablets during a drug treatment period of up to 50 weeks.


Secondary Objectives
	
 • To evaluate the safety of nalbuphine by achieved maintenance dose at the end of Treatment Week 4. • Assess skin lesion improvement using the metrics of the PAS • Change from Baseline in Patient-Reported Outcome measures Worst (i.e., most severe itching over the past 24 hours) itch NRS, average itch intensity NRS, VRS (itchy, burning and stinging), MOS Sleep-R, ItchyQoL, HADS by the final Treatment Period Visit • Change between Baseline and the final Treatment Period Visit in PBI-P • A description of the frequency and reasons for dose up- and down-titration and treatment discontinuation during the study • Frequency and distribution by time on study of patients determined to meet failure-to-improve criteria • Changes in the PRO measurements during the Washout Period after cessation of treatment of nalbuphine HCl ER tablets • Time to first use of rescue medications and the number of days of use of rescue medications for itching • To evaluate the daily changes in the Subjective Opiate Withdrawal Scale (SOWS) during the Washout Period after cessation of treatment of nalbuphine HCl ER tablets.

Exploratory Objectives
	
A single exploratory objective of the study is to evaluate:
 
 • The potential of nalbuphine HCl ER tablets to impact on the measurement of nerve fiber density (histology) and MOR/KOR density (histology, Western Blot), as well as histological (H&E) changes in skin biopsies taken at Baseline and by the final Treatment Period Visit to investigate possible correlation with any clinical response and also compared to biopsy material assessed during study TR03 (optional procedures at select sites only).

Selection Criteria
	
Inclusion Criteria:
 
Patients must meet all of the following criteria to be eligible:
 
 1. Have been adequately informed of the nature and risks of the study and have given written informed

	
consent at or prior to Visit 1a.
 
 2. Have completed participation in the TR03 study. Completion of participation in the TR03 study is defined as completion of Study Drug treatment through TR03 Visit 5 and completion of the TR03 Visit 6. 3. Agree to comply with the contraception requirements as below: Female patients of childbearing potential are required to use one barrier method (e.g., condom, cervical cap, or diaphragm) of contraception in addition to one other method (e.g., intrauterine device [IUD], hormonal contraception, tubal ligation, Essure procedure, or spermicide). For the purpose of this study, all females are considered to be of childbearing potential unless they are post-menopausal (i.e., at least 1 year since last menses and age >50 years) or surgically sterile (i.e., tubal ligation, hysterectomy and/or bilateral oophorectomy). 4. Ability and acceptance to provide written informed consent. 5. Willing and able to comply with study requirements and restrictions 6. Agree to the confidential use and storage of all data (including photography) and use of all anonymized data for publication including scientific publication.

Selection Criteria
	
Exclusion Criteria:
 
If a patient meets any of the following criteria, he or she is not eligible:
 
 1. Patients with a history of congestive heart failure of Class 2 or higher as graded using the New York Heart Association scale (scale provided in Appendix 5) 2. Patients with a history of angina pectoris grade 2 or higher as graded using the Canadian Cardiovascular Society grading scale (scale provided in Appendix 5) 3. History of ventricular tachycardia, torsade de pointes, family history of sudden death, myocardial infarction or acute coronary syndrome within the previous 3 months, as reported by the patient. 4. Serum potassium below the laboratory lower limit of normality. Potassium supplementation can be prescribed and the serum potassium level repeated 5. QTcF interval >450ms on screening EKG 6. Heart rate <50 BPM on screening

	
 7. Use of a medication known to be associated with risk of torsade de pointes (see Section 9.7.8, Safety Assessments, for hyperlink to the CredibleMeds Filtered QTDrug List for cardiovascular related prohibited medications with a known associated risk of Torsade de Pointes) 8. History of substance abuse within the past year as determined by the Investigator 9. Significant medical condition or other factors that in the opinion of the Investigator may interfere with the conduct of the study 10. Known hypersensitivity or allergy to nalbuphine or formulation components 11. Is a pregnant or lactating female
Study Treatment Allocation	All patients who are enrolled into the study will receive active treatment with nalbuphine HCl ER tablets.
Study Procedures	
Visit 1a of the TR03ext study is temporally the same visit as TR03 Visit 6. Subjects who do not consent by the end of the TR03 study visit 6 are no longer eligible for the extension study. Study TR03 Visit 6 procedures in common with Study TR03ext Visit 1a procedures do not have to be repeated.
 
For All Patients:
 
For all patients, TR03ext Visits (both during the Treatment Period and Observation Period) will include recording of vital signs, completion of PRO questionnaires, assessment of AEs, and recording of concomitant medications.
 
On Visit 1a, patients will either enter directly into the drug Treatment Period or into a no-drug Observation Period based on their reported Worst itch NRS scores (defined as most severe itching over the past 24 hours) on that Visit day.
 
Patients with a Worst Itch NRS score greater than or equal to 5 (\geq) 5 enter the Treatment Period:
 
Patients with Worst itch NRS \geq 5 at Visit 1a will start in the drug Treatment Period of the study and will receive Study Drug starting with an evening 30 mg dose (to be taken at home), after the Treatment Visit 1a procedures have been completed. Receipt of the first dose of study drug will define Treatment Period Day 1. Treatment Visit 1a for these patients is also Treatment Visit 1 (TV1). Subsequent visits will be defined as TV2, TV3, etc. In addition, during the time period of dose titration, information will be obtained via telephone communication; these will be defined as TC1, and TC2.
 
The dose will be titrated for up to 4 weeks based on tolerability, after which time the dose achieved (as of the end of Treatment Week 4) will be maintained up to an additional 46 weeks (with the exception of permitted down titrations);

see [Table 3](#) Study Drug Dosing schedule.

For patients transitioning from the Observation period, the total time in the Treatment Period plus any time in the Observation Period will be a total of 50 weeks.

Safety laboratory data and blood for PK, ECGs (locally and centrally read), and physical examinations including the PAS assessment will be performed periodically according to the Schedule of Events (See [Appendix 1](#)). Schematic descriptions of the study can be found in [Appendix 2](#).

All patients on drug treatment will enter a 2-week wash-out and safety follow up period following end of the Treatment Period with procedures conducted according to the Schedule of Events (See [Appendix 1](#)).

Patients with a Worst Itch NRS score less than 5 (< 5) enter the Observation Period:

Patients with a Worst Itch NRS score < 5 at Visit 1a will enter into an extended screening period, Observation Period (no drug treatment), of the study and will be followed for up to 12 weeks (extended screening weeks). Visit 1a for these patients is also Observational Visit 1 (OV1). Subsequent visits will be defined as OV2, OV3 and OV4 and will occur at approximately monthly intervals for the next 3 months.

During this Observation period, patients who report an increase in their Worst Itch NRS with a score of ≥ 5 at any one of their Observation Visits and meet all other eligibility criteria will be able to enroll immediately into the Treatment Period of the study and Visit 1b procedures are to be performed. Patients will receive open-label Study Drug starting with an evening 30 mg dose (to be taken at home), after the Visit 1b procedures have been completed. Receipt of the first drug will indicate the start of their Treatment Period and enrollment into the study. The duration of the Treatment Period for such a patient will vary depending upon the visit at which they transition from the Observation Period to the Treatment Period.

Patients in the Observation Period whose Worst Itch NRS score remains <5 over the 12 extended screening weeks will be screen failed from the study at the end of that time period.

Failure to Improve Criteria:

Beginning on TV 3 and at every subsequent Treatment Visit, patients with a Worst itch NRS equal to or greater than (\geq) the Worst Itch NRS at Visit 1a (or at Visit 1b in the case of patient who require the Observation Visit period) will be discontinued from taking study drug. Subjects discontinued from taking study drug are to undergo the End of Treatment Visit (TV14), the Washout/Safety Follow-up Period assessment in two weeks and receive a follow-up Telephone Contact 30 days following end of study drug for final safety

	assessment.
Safety Assessments	
Safety will be assessed based on adverse events (AEs), clinical laboratory measurements, Investigator review and central cardiac core laboratory read-12-lead electrocardiogram (ECG), vital signs and physical examinations.
 
An unblinded, independent Data Safety Monitoring Board (DSMB) will periodically review safety data. The frequency of data review and DSMB processes are outlined in the DSMB charter.

Efficacy Assessments	
Efficacy Measurements:
 
 • Worst itch intensity (from NRS) • Average itch intensity (from NRS) • VRS (itchy, burning and stinging) • ItchyQoL • MOS Sleep-R • HADS • PAS • PBI-P • Frequency, pattern, and reasons for dose titration • Use of rescue medications for itching 
At selected sites (optional procedures):
 
 • Nerve fiber density (histology) at Baseline and the final Treatment Period Visit • MOR/KOR density (histology, Western Blot) at Baseline and the final Treatment Period Visit • Histological analysis (H&E) at Baseline and the final Treatment Period Visit
Pharmacokinetic Assessments	
Blood samples for nalbuphine plasma concentration (and metabolites as needed) will be collected periodically according to the Schedule of Events (Appendix 1).

Study Endpoints	
Primary Endpoint:
 
 • A description of the incidence and nature of TEAEs during Treatment Weeks 5- 50 
Secondary Endpoints
 
Visit 1a or 1b will serve as the baseline visit for efficacy endpoints. Visit 1a will be the baseline for patients directly entering the Treatment Period as of Visit 1a. Visit 1b will be the baseline for patients entering the

	
Treatment Period after participating in the Observation Period for any length of time.
 
 • Assess skin lesion improvement using the metrics of the PAS • Change from Baseline in Patient-Reported Outcome measures Worst itch NRS, average itch intensity NRS, VRS (itchy, burning and stinging), MOS Sleep-R, ItchyQoL, HADS) by Treatment Period study visit and Baseline NRS score • Change between Baseline and final Treatment Period visit in PBI-P • A description of the percentage of patients utilizing various doses of nalbuphine HCl ER tablets by Study Week • A description of the frequency and reasons for dose up- and down-titration and treatment discontinuation during the study • Frequency and distribution by time on study of patients determined to meet failure to improve criteria • Changes in the PRO measurements during the Washout Period after cessation of treatment of nalbuphine HCl ER tablets • Time to the first use of rescue medications and the number of days of use of rescue medications for itching • To evaluate the daily changes in the Subjective Opiate Withdrawal Scale (SOWS) during the Washout Period after cessation of treatment of nalbuphine HCl ER tablets 
Exploratory Endpoint
 
 • Impact on the measurement of nerve fiber density (histology) and MOR/KOR density (histology, Western Blot), as well as histological (H&E) changes in skin biopsies taken at Baseline and the final Treatment Period Visit to investigate possible correlation with any clinical response and also compared to biopsy material assessed during study TR03 (optional procedures at select sites only).

Statistical Methodology
	
Efficacy:
 
All efficacy endpoints will be evaluated through the generation of summary statistics. For continuous variables, the mean, standard deviation, median, minimum, and

maximum will be presented for a particular visit and for the change from baseline (Visit 1a or 1b). For categorical variables, the number and percentage of patients within each category of classification will be summarized by study visit. No formal statistical testing will be conducted.

Safety:

The incidence of AEs will be summarized through the presentation of proportions by MedDRA body system classification and preferred term. Vital signs and laboratory data will be summarized using continuous-based descriptive statistics (n, mean, SD, median, minimum, maximum). The extent and duration of use of rescue medications will be similarly summarized using descriptive statistics. Summary statistics for AEs with onset during the Observation Period will be separately summarized. No formal statistical analysis will be performed on safety outcomes; inferences, if any, will be derived through clinical review and interpretation.

TABLE OF CONTENTS

1	STUDY SYNOPSIS	5
	TABLE OF CONTENTS	13
	LIST OF TABLES	16
	LIST OF FIGURES	16
2	LIST OF ABBREVIATIONS	17
3	INTRODUCTION	19
3.1	PRURIGO NODULARIS AND STUDY RATIONALE	19
3.1.1	General Information on Prurigo Nodularis	19
3.1.2	Potential Mechanism of Prurigo Nodularis Pathophysiology	21
3.1.3	Rationale for Investigating Nalbuphine HCl ER in Prurigo Nodularis	24
3.2	NALBUPHINE	27
3.3	NALBUPHINE HCL ER TABLET CLINICAL DEVELOPMENT	28
3.3.1	Overall Summary	28
3.3.2	Clinical Study TR01 in Hemodialysis Patients and Healthy Volunteers	29
3.3.3	Additional Nalbuphine HCl ER Tablet Clinical Data	31
4	STUDY OBJECTIVES	32
4.1	PRIMARY OBJECTIVE	32
4.2	SECONDARY OBJECTIVES	32
4.3	EXPLORATORY OBJECTIVES	32
5	STUDY ENDPOINTS	33
5.1	PRIMARY ENDPOINT	33
5.2	SECONDARY ENDPOINTS	33
5.3	EXPLORATORY ENDPOINTS	33
6	NUMBER OF SITES AND PATIENTS	34
7	ESTIMATED STUDY DURATION	34
8	SELECTION CRITERIA	34
8.1	STUDY POPULATION	34
8.2	INCLUSION CRITERIA	34
8.3	EXCLUSION CRITERIA	35
9	STUDY PLAN	35
9.1	GENERAL STUDY DESIGN	35
9.2	RATIONALE FOR STUDY DESIGN	35
9.3	SAFETY MONITORING PLAN	37
9.4	RISK-BENEFITS	39
9.5	STUDY OVERVIEW	40
9.6	STUDY PROCEDURES	42
9.6.1	Visit 1a (Day 1 of Study Week 1)	43
9.6.2	Treatment Period (Treatment Weeks 1-50)	45
9.6.3	Observation Period (Extended Screening Weeks 1-12)	58
9.6.4	Transition to Treatment Period (Visit 1b)	59
9.6.5	Washout and Safety Follow-Up Period	61

9.6.6	Premature Discontinuation of Study Drug Follow-up Telephone Contact Visit	62
9.6.7	Early Termination Visit for Patients who Withdraw Consent.....	62
9.6.8	Unscheduled Visits	63
9.6.9	Schedule of Events.....	63
9.7	STUDY DRUG TREATMENT AND DRUG ACCOUNTABILITY.....	63
9.7.1	Study Drug Dosing	63
9.7.2	Down-Titration	66
9.7.3	Multiple Missed Doses	66
9.7.4	Overdose	66
9.7.5	Treatment Compliance.....	66

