17. My itchy skin condition makes me angry or irritable.	 1	 2	 3	 4	 5
18. My itchy skin condition makes me feel depressed or sad.	 1	 2	 3	 4	 5
19. I worry about what other people think about me because of my itchy skin condition.	 1	 2	 3	 4	 5
20. I worry that the itching will last forever.	 1	 2	 3	 4	 5
21. I feel self-conscious because of my itchy skin condition.	 1	 2	 3	 4	 5
22. My personality has changed because of my itchy skin condition.	 1	 2	 3	 4	 5

Subject signature

Date

Prurigo Activity Score (PAS)

Sample – actual assessment scale will be provided to the patient at appropriate visits

1. Type
 
a) Which efflorescences do you see?
 
 papules  nodules  plaques  umbilicated ulcers  hypo-/hyperpigmented maculae
 
b) Which type of prurigo is predominant?
 
 Prurigo papular type  Prurigo nodular type  Prurigo plaques type  Prurigo umbilicated "Kyrle" type  completely healed
	
2. Number
 
a) How many Prurigo lesions do you see? (do not count scars)
 
 0  1 - 19  20 – 100  > 100
 
3. Distribution:
 
 disseminated  localized (only 1 or 2 areas affected)  neither of them
																		

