
4. Please mark the affected area(s) (for definition of trunk see image).
 
whole body except head 
 
whole body head included 
 
or
 
forearm:  left  right upper arm:  left  right lower leg:  left  right upper leg:  left  right trunk:  ventral  dorsal head:  capillitium  face
 	
5. Please choose a representative area:
 
forearm:  left  right upper arm:  left  right lower leg:  left  right upper leg:  left  right trunk:  ventral  dorsal
 
Number of prurigo lesions in representative area (do not count scars): _____
																		

6. Monitor lesions. Please mark the biggest (B) and a representative (R) prurigo lesion (remains the same in every visit).
 
  
 	Highest elevation [mm]	Biggest diameter [mm]	
 
 longitudinal	crosswise	
   
 biggest prurigo lesion				
 
 representative prurigo lesion				
  
			Highest elevation [mm]	Biggest diameter [mm]		longitudinal	crosswise	biggest prurigo lesion				representative prurigo lesion							
	Highest elevation [mm]			Biggest diameter [mm]															
		longitudinal	crosswise																
biggest prurigo lesion																			
representative prurigo lesion																			

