In order to facilitate analysis of the clinical safety data and efficacy data, patients in the present study will begin titration at the 30 mg QD dose and titrate to only a maintenance dose ranging between 30 mg BID and 180 mg BID. The 30 mg BID and 60 mg BID doses are believed to be only marginally effective doses based on available TR01 data. However there is a two time dose reduction permitted for all subjects during Treatment Weeks 5-50 (see [Table 3](#)) to the next lower allowed dose (e.g., a subject at the 90 mg BID maintenance dose will be permitted a dose reduction to 60 mg BID or subsequently to 30 mg BID and then be maintained at that dose level for the remainder of the study).

The study population being evaluated is an intended target population for oral nalbuphine HCl ER tablets: prurigo nodularis patients.

Patients will be closely monitored for safety. All patients will be seen at the Investigator site (See [Schedule of Events in Appendix 1](#)). Adverse events and vital signs will be recorded. Additionally, 12-lead ECGs (locally and centrally read), physical examinations, and clinical laboratory testing will be conducted to monitor safety on patients receiving study drug. Safety monitoring will be done to address the primary objective of evaluating the longer term safety of study drug exposure. The primary endpoint is a description of adverse events during up to 50-weeks of treatment with nalbuphine HCl ER tablets. An important secondary endpoint objective of the study is to use recorded PAS metrics to assess the study drug anti-pruritic suppression of the scratching behavior of the subject and impact on skin lesion improvement. Changes in patient-reported outcome measures: Worst itch NRS, Average itch intensity NRS, VRS (itchy, burning and stinging), ItchyQoL, MOS Sleep-R, HADS and PBI-P will be explored.

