9.6.2.2.6 TV 8 (Treatment Week 26)

The following procedures are to take place at this visit:

- Administer the Worst Itch NRS and evaluate against the Failure-to-Improve criteria (see [Section 11.1](#))
- For patients who MEET the Failure-to Improve criteria
 - Stop study medication
 - Perform End of Treatment Visit (TV14) procedures
- For patients who DO NOT meet Failure-to-Improve perform the following procedures
 - obtain vital signs

- perform physical examination
- perform brief neurological assessment
- complete the PAS
- perform 12-lead ECG after at least 5 minutes in a supine position (See the Study Reference Manual for ECG procedures, [section 17.4](#) Electrocardiograms for the handling of Cardiovascular adverse events)
- collect urine for pregnancy test (must be confirmed negative prior to dispensing study drug)
- collect urine for urinalysis for central lab
- collect blood for central laboratory (hematology and chemistry) and for PK
- administer PRO measurements:
 - Average itch intensity NRS
 - VRS
 - ItchyQoL
 - MOS Sleep-R
 - HADS

The PRO questionnaires must be administered at the study site under the supervision of and by trained study staff, strictly adhering to PRO Administration Instructions (see Study Reference Manual).

- record AEs
- review concomitant medications, including over-the-counter medications, nutritional supplements, and vitamins
- reinforce compliance
- perform study drug accountability, retrieve previously dispensed study drug
- dispense study drug to the patient required until the next Treatment Visit

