9.7.7.7 Prurigo Activity Score (PAS)

The PAS consists of 7 quantitative and quantitative measurements related to the examination of the skin. Type, number, distribution, affected body parts, and quantitative number of lesions in a representative body part are documented. The biggest lesion and the most representative lesion are monitored with documentation of height and area measurements. Prurigo lesion activity is recorded as a percentages based on their stage (0-4). Photographs of the body are conducted with monitored lesions marked. The instrument can be found in [Appendix 4](#). Please see the Study Reference Manual for instructions for obtaining and storing photographs collected in conjunction with the PAS.

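### For the categorical PAS items, per-visit percentages set all treated patients at Baseline against a selected group at Week 26, with no within-patient change stated

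*Protocol*

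**What the plan says.** The Version 2.0 synopsis lists among the secondary endpoints: "Assess skin lesion improvement using the metrics of the PAS". Section 9.2 gives this weight: "An important secondary endpoint objective of the study is to use recorded PAS metrics". The same section uses possible lesion healing as a reason for the length of the study.

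The Statistical Methodology entry of the synopsis has two rules. One is for continuous variables, whose usual summary statistics are promised in two forms: "maximum will be presented for a particular visit and for the change from baseline (Visit 1a or 1b"). The other has no counterpart to the second form: "For categorical variables, the number and percentage of patients within each category of classification will be summarized by study visit". Section 19.8.1 of Version 1.0 has the same pair of rules. Section 19 of Version 2.0 is not in the text at hand.

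Section 9.7.7.7 describes activity on the PAS: "Prurigo lesion activity is recorded as a percentages based on their stage (0-4"). The instrument is printed in Appendix 4 of Version 1.0.

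The PAS is done at Visit 1a or 1b, at TV8 (Treatment Week 26), at TV14 and, in Version 2.0, at the Early Termination Visit. In Section 9.6.2.2.6 the TV8 PAS stands under this condition: "For patients who DO NOT meet Failure-to-Improve perform the following procedures". From TV3 onward, patients whose Worst Itch NRS is at or above their own baseline stop study drug and undergo TV14 procedures.

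**The concern.** Improvement is a statement about the same patient at two times. A percentage per category at each visit can show it only if the same patients stand in both columns. Here every treated patient contributes to Baseline, while the Week 26 column holds those who have come through six checks (TV3 to TV8) and have not stopped for any other reason.

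The study has no control arm, so nothing separates a real shift in stage from a change in who is left. A reader who sees the share in stages 3-4 fall between Baseline and Week 26 would naturally read it as healing. The items concerned are the ones that speak most directly to scratching (excoriations and crusts) and to healing.

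**Working it through.** The protocol gives no stage distribution, dropout rate or calculated sample size, so there is no figure of its own to reproduce.

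**Step 1. Which rule covers which PAS item**

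| PAS item (Version 1.0, Appendix 4) | Form | Summary under the stated rules |
|---|---|---|
| Excoriation/crust stage | ordinal, 0-4 | n (%) by visit |
| Healed-lesion stage | ordinal, 0-4 | n (%) by visit |
| Total lesion number | bands 0, 1-19, 20-100, >100 | n (%) by visit |
| Lesion count in a representative area | numeric | by visit and change from baseline |
| Elevation and diameters of two monitored lesions | numeric | by visit and change from baseline |

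The point concerns the first three rows.

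**Step 2. Who is in each column**

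Baseline: all treated patients (Visit 1a or 1b). Week 26: those still on drug who do not meet the failure-to-improve criterion that day. Patients who stop before then, or at TV8 under that criterion, have their PAS recorded as TV14. They are in the first column and not in the second.

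**Step 3. Size of the artefact when no stage changes**

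Assumptions: share in stages 3-4 at Baseline b = 0.60; fraction stopped by Week 26 q = 0.50 or 0.30; stop ratio R (stages 3-4 against stages 0-2) from 3 down to 0.5.

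- Stop probability in stages 0-2: s = q / (bR + 1 - b)
- Share in stages 3-4 at Week 26: b(1 - Rs) / (1 - q)

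With q = 0.50 and R = 2: s = 0.50 / (1.2 + 0.4) = 0.3125, so Rs = 0.625 and the share is 0.60 × 0.375 / 0.50 = 45.0%.

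With q = 0.50 and R = 0.5: s = 0.50 / (0.3 + 0.4) = 0.714, so Rs = 0.357 and the share is 0.60 × 0.643 / 0.50 = 77.1%.

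| Stop ratio R | Week 26 share, q = 0.50 | Week 26 share, q = 0.30 |
|---|---|---|
| 3 | 38.2% | 50.6% |
| 2 | 45.0% | 53.6% |
| 1.5 | 50.8% | 56.0% |
| 1 | 60.0% | 60.0% |
| 0.5 | 77.1% | 67.3% |

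At R = 3 the apparent improvement is 22 points with half stopped and 9 points with 30% stopped. At R = 0.5 there is an apparent worsening of 17 and 7 points.

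**Step 4. The same data, paired**

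If Baseline is restricted to patients with a Week 26 PAS, each share in Step 3 appears in both columns and the change is 0 in every row.

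**Step 5. Is loss of this order plausible?**

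The failure-to-improve rule was simulated alone over TV3 to TV8. Assumed were a mean NRS of 7 to 8, between-patient SD 1.5, within-patient SD 1.0 to 1.5, independent visit errors and entry at NRS of at least 5. A true fall of 2 points retained 39% to 60% of patients through TV8, and a fall of 3 points retained 63% to 87%. Losses of 30% to 50% lie within what the rule could produce, but these inputs are also assumptions.

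**The case against.** The strongest objection is that shift tables for ordinal items are ordinary analysis-plan content. Section 19.1 of Version 1.0 leaves the detail of the summaries to that plan, and nothing forbids a paired table. Section 19 of Version 2.0 is also not in the text at hand. This limits the point to what the protocol states, but does not remove it. The protocol is not silent: it gives change from baseline to one type of variable and per-visit percentages to the other.

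Section 19.8.1 of Version 1.0 also requires a baseline and a post-baseline value so that change can be calculated. That shows within-patient change was in mind. It does not align the columns, because a TV14 PAS makes an early stopper eligible without any Week 26 value.

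Three objections on scope stand in full:

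- A reader might infer that the PAS as a whole cannot show within-patient improvement. It can: the representative-area count and the monitored-lesion measurements are numeric and receive change from baseline.
- A reader might extend the point to the VRS. The secondary endpoints already specify change from Baseline for it.
- A reader might infer that attrition will mimic healing. The stopping rule compares itch with the patient's own baseline and does not use lesion stage, so loss may run either way or be unrelated to stage.

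In addition, patients who stop drug have a PAS at TV14, and those who withdraw consent have one at Early Termination if feasible. The end-of-treatment comparison therefore covers largely the same patients as Baseline.

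**Conclusion.** The point holds for three categorical PAS items (excoriation/crust stage, healed-lesion stage, banded lesion number), and chiefly at Week 26. For these, the stated rule compares all treated patients with a selected group and offers no within-patient summary. Under the assumed inputs, with no lesion changing and half the patients stopped, a Baseline share of 60% in stages 3-4 could read anywhere from 38% to 77% at Week 26. With equal stopping it stays at 60%.

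The stage mix, the fraction stopped and the stop ratios are all assumed. An artefact needs loss related to lesion stage. That is plausible, since the protocol itself links itch, scratching and lesions, but it is not established. The documents support saying that the Week 26 percentages can mislead in either direction, not that they will show false healing. The endpoint is secondary and descriptive, with no formal testing, so the change is worth making but the primary safety objective is untouched.

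**What to change.** Add to the rule for categorical variables, in the synopsis and the matching text of Section 19.8.1, for these three PAS items:

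- a Baseline-by-visit shift table in patients with both assessments;
- n (%) improved by at least one category, unchanged and worsened in those patients;
- the Baseline distribution of those same patients beside the visit distribution.

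Report these at Week 26 and at the end-of-treatment PAS (TV14 or Early Termination), with the number of patients at each.

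The cost is a sentence in each place and a few tables. No new data are collected. The downside is that the paired Week 26 table uses fewer patients than the full Baseline column.
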